**Physical Examination**

Physical examinations will be performed according to the Time & Events Schedules (see [Table 1](#) and [Table 2](#)) with attention to areas of potential tumor involvement (including enlargement of liver and spleen). Any clinically significant observations should be recorded on the Adverse Event page of the CRF. Any clinically significant abnormalities persisting at the end of treatment will be evaluated by the investigator until resolution or until reaching a clinically stable endpoint.

**ECG Assessment**

ECG will be performed and analyzed locally. Subjects entering the study naïve to siltuximab will have ECGs performed according to the Time and Events Schedules (see [Table 1](#) and [Table 2](#)). A focused cardiac investigation including an ECG is recommended if clinically indicated for any subject during the study.

### **9.3 Efficacy Evaluations**

#### **9.3.1 Disease Control**

Investigator assessment of disease control will be collected during screening, at Cycles 4, 7, and 10, every 6 months thereafter, and at study treatment discontinuation (or Follow-up Week 4 visit).

Disease assessments listed in [Attachment 2](#) (including cutaneous assessments), are provided as a guide for assessing multicentric Castleman's disease. If a subject shows disease progression at 2 consecutive assessments the subject must discontinue study treatment.

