
a. Siltuximab should be administered after all other study assessments and evaluations required at that visit. The visit window for siltuximab administration is minus 3 or plus 4 days from the scheduled visit date.
 
b. Blood samples for biomarker testing should be collected prior to study agent administration and at the end of treatment visit. A frequency of every 12 weeks means every 4th cycle for those on an every 3-week administration schedule and every 2nd cycle for those on an every 6-week administration schedule.
 
c. Scheduled blood samples for testing antibodies to siltuximab should be collected prior to study agent administration. Serum from venous blood samples (7.5 mL per sample) will be split into 3 aliquots (1 aliquot for analysis of antibodies to siltuximab, 1 aliquot for siltuximab serum concentration analysis to code antibodies to siltuximab data, and 1 aliquot as a backup). Serum concentration of siltuximab will also be determined at these timepoints. In addition, an unscheduled blood sample should be drawn, if possible, for determining antibodies to siltuximab any time an infusion-related reaction is observed during the study. This sample should be obtained as soon as possible after the reaction. A frequency of every 12 weeks means every 4th cycle for those on an every 3-week administration schedule and every 2nd cycle for those on an every 6-week administration schedule.
 
d. Serum samples for glycoform clearance analysis and in vivo protein degradation will be collected from 5 former study C0328T03 subjects (administered 11 mg/kg every 3 weeks) who consented to have these samples collected. These samples should be collected Cycle 1 (pre- and post-dose), and at Cycle 1 Day 3, Week 1 (Day 7 +/- 1 day), Week 2 (Day 14 +/- 2 days), and Week 3 (Day 21 +/- 2 days; before the Cycle 2 dose).
 
e. Vital signs will be measured predose and end of infusion on Day 1 of Cycle 1. Thereafter, vital signs will be measured only before each study agent administration on Day 1 of each cycle, and as clinically indicated.
 
f. ECGs will only be performed for those subjects who are siltuximab naïve at study entry, and as clinically indicated for all subjects.
 
g. Hematology and chemistry panel has to be performed prior to first dose to assess the subject's eligibility. If screening takes place within 7 days prior to first dose, the tests are not required to be repeated pre-dose Cycle 1. Laboratory monitoring will occur prior to each infusion in the first year of treatment for those subjects that are siltuximab-naïve at study entry.
 
h. Fasting sample is required at screening and preferred for subsequent samples. If lipid panel is abnormal, amylase and lipase may be assessed as clinically indicated.
 
i. Coagulation parameters should only be evaluated if clinically indicated.
 
j. If last chest X-ray was performed within 3 months prior to first dose, results can be used for the screening timepoint. If equivalent imaging (ie, CT, MRI) was performed for routine medical care at the timepoint, it is allowed instead of chest X-ray.
 
k. If considered to be clinically indicated, investigator assessment along with ESR, CRP, and fibrinogen evaluations, should be performed more frequently. Quantitative immunoglobulins should be performed if clinically indicated. Subjects who demonstrate disease progression on an once every 6 weeks dosing schedule (see Section 6.1) have to return to the every 3 weeks dosing schedule after reassessment of hematology and chemistry lab panels, physical exam, and, if not done within last 6 weeks, also a reassessment of investigator assessment of disease control and ESR, CRP, and fibrinogen.
 
l. Survival status after 5-year data cutoff will be collected twice a year for subjects still on treatment provided by Sponsor. For these subjects, SAEs, concomitant medications involved in treatment of SAEs, and information on pregnancies will continue to be collected. After treatment discontinuation, survival status, occurrence of malignancies, and subsequent therapies for MCD will be collected twice per year.
 
m. Only for subjects from the C0328T03 study; to be performed at the start of the screening visit, and predose at Cycles 1 and 2 (before other procedures).
							

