## 6 DOSAGE AND ADMINISTRATION

Siltuximab will be given as a 1-hour infusion at 11 mg/kg every 3 weeks. All subjects will be treated until they progress, withdraw, experience unacceptable toxicity, or until the 6-year data cutoff, whichever comes first. A data cutoff will occur approximately 6 years after the start of enrollment; however, continued drug supply will be ensured for study subjects who would not otherwise have access to siltuximab.

Subjects with confirmed partial or complete remission, defined as a documented radiographic response, for more than 6 months (including those entering the study in PR or CR) may be dosed every 6 weeks at the investigator's discretion. Demonstration of radiographic response is not required for subjects with skin-only disease with confirmed PR/CR for more than 6 months. Subjects on the 6-week schedule should be monitored for safety and disease assessment evaluations as per protocol Time & Events Schedules (see [Table 1](#) and [Table 2](#)). When disease progression is suspected, all screening and pre-dose Cycle 1 evaluations should be repeated and treatment with siltuximab could continue at 11 mg/kg siltuximab every 3 weeks. The effective switch from the 3-week dosing schedule to the 6-week schedule can only occur on odd-numbered cycle visits to match the collection timepoints of biomarkers and immunogenicity samples of every 12 weeks, and has to occur on dosing days. Switching back to a 3-week schedule upon suspected disease progression can occur at any cycle visit.

During the study, no dose modifications of siltuximab will be allowed. Dose delays of up to 3 weeks will be allowed for treatment-related toxicity. Documentation of dose delays, including the reasons for the delay, is required.

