## ATTACHMENT 2: DISEASE ASSESSMENTS

Disease assessment criteria (including cutaneous disease assessments) are provided as a guide for the investigator.

Each subject can be classified as stable, improved, or worsened based on hemoglobin, fatigue, anorexia, fever, weight, and target lymph node assessment (see the first table below). If a subject improves in at least one measure and remains stable for all other measures, the subject is considered to have improved. A worsening in any of the measures will be considered as a progression of the disease. Any other subject will be considered stable for clinical benefit. The investigator's assessment of all lymph node radiologic results will also be recorded.

For subjects who have only cutaneous disease (cutaneous disease must be proven by biopsy), the response assessment for cutaneous lesions is a modified physician's global assessment that has been used in previous oncology clinical studies (Duvic et al, 2001a; Duvic et al, 2001b) and will be one of the clinical benefit components, and be assessed based on the following response criteria.

The extent of disease will be measured by an estimation of BSA involved; single sites of disease must be > 1 cm in diameter. Twelve main body areas will be assessed, as listed in the second table below (Duvic et al, 2001c).

Clinical Benefit Assessments for Castleman's Disease			
Measure	Status		
	Improved	Stable	Worsening
Hemoglobin	Increase of at least 2 g/dL relative to baseline without blood transfusion	Less than 2 g/dL variance relative to baseline without blood transfusion	Decrease of at least 2g/dL relative to baseline without blood transfusion
Fatigue	Decrease of at least 1 CTC grade point relative to baseline	No change in CTC grade relative to baseline	Increase of at least 1 CTC grade point relative to baseline
Anorexia	Decrease of at least 1 CTC grade point relative to baseline	No change in CTC grade relative to baseline	Increase of at least 1 CTC grade point relative to baseline
Fever*	Decrease of at least 2°C relative to baseline or return to normal body temp (37°C)	Less than 2°C variance relative to baseline unless normal body temp is achieved then define as improved	Increase of at least 2°C relative to baseline

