5.2.3. Duration of Disease Control

5.2.3.1. Definition

For subjects who had/experienced disease control, duration of disease control (DODC) is defined as the time from the first siltuximab administration to disease progression as assessed by the investigator. Subjects with disease control are subjects who had stable or better response assessed by the investigators. Subjects without disease progression will be censored at the date of last disease assessment. Note that disease control was only collected in long-term safety extension study of CNT0328MCD2002.

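### The protocol's stopping rules on progression conflict, and the SAP does not say whether a single or a confirmed progression ends disease control

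*Protocol*

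**What the plan says.** **Treatment rules.** Protocol Section 6 states: "All subjects will be treated until they progress, withdraw, experience unacceptable toxicity, or until the 6-year data cutoff, whichever comes first". The Synopsis, Sections 3.1 and 10.2, and SAP 1.1 repeat this. Section 10.1 gives disease progression as its example of a clinical endpoint after which a subject counts as having completed the study. Section 9.3.1 sets a different trigger: "If a subject shows disease progression at 2 consecutive assessments the subject must discontinue study treatment". The itemised list of reasons to discontinue in Section 10.2 does not include progression, although the opening sentence of that section does.

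**6-weekly dosing.** After describing the 6-weekly schedule, Section 6 says that when progression is suspected, the screening and pre-dose evaluations are repeated and "treatment with siltuximab could continue at 11 mg/kg siltuximab every 3 weeks". Footnote k of Table 1, the schedule through Amendment INT-3, goes further: "Subjects who demonstrate disease progression on an once every 6 weeks dosing schedule (see Section 6.1) have to return to the every 3 weeks dosing".

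**What progression is.** Attachment 2 says: "A worsening in any of the measures will be considered as a progression of the disease". It also limits its own status: "Disease assessment criteria (including cutaneous disease assessments) are provided as a guide for the investigator".

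**Endpoints.** SAP 5.2.3.1 defines duration of disease control as "the time from the first siltuximab administration to disease progression as assessed by the investigator", and protocol 11.4.1 agrees. SAP 5.2.1.1 counts a prior responder as maintaining control if the investigator's assessment shows no progression during the extension. SAP 5.2.2.1 defines control in siltuximab-naïve subjects through a stable or better response and does not use progression.

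**The concern.** A subject with one recorded progression falls under incompatible instructions: stop now, or stop only if the next assessment also shows progression. Different sites can reasonably act differently. The choice affects more than treatment. Section 3.1 limits data collection after study agent stops to survival, malignancies and subsequent MCD therapy. A site that stops at the first progression therefore produces no later disease assessment beyond the end-of-treatment visit, while a site that waits does.

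The SAP does not resolve this. It uses progression as the event without saying whether one progression call is enough, which date applies if two are needed, or how a subject is counted who progresses on 6-weekly dosing and continues treatment. Two analysts could obtain different values for the proportion maintaining control and for its duration from the same data. Those values could also depend in part on which stopping rule each site followed.

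**Working it through.** The plan states no figure to reproduce: the sample size is not calculated and no test is planned. The check is a comparison of passages, followed by an illustration of size.

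**One subject under each passage.** Take a subject on 3-weekly dosing whose investigator records progression at Cycle 7 and who would be stable at Cycle 10.

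| Passage | Consequence |
|---|---|
| Protocol 3.1, 6, 10.2; SAP 1.1 | Treatment ends at Cycle 7; Cycle 10 is not assessed |
| Protocol 10.1 | Progression precludes further study |
| Protocol 9.3.1 | No mandatory stop at Cycle 7, nor at Cycle 10 |
| SAP 5.2.1 and 5.2.3, single progression | Control lost; event at Cycle 7 |
| SAP 5.2.1 and 5.2.3, confirmed progression | No event if Cycle 10 was assessed; undefined if it was not |

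**Visit calendar.** Cycle c starts 3(c − 1) weeks after Cycle 1 on 3-weekly dosing, so Cycles 4, 7 and 10 fall at weeks 9, 18 and 27. On 6-weekly dosing they fall at weeks 18, 36 and 54. Assessments are 6-monthly after that. If a sustained progression were dated at the second call instead of the first, the event would move by about 9 weeks early on (18 weeks on 6-weekly dosing) and by about 6 months later.

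**Number of visits.** Week 27 is 27 / 4.348 = 6.2 months. By 72 months, (72 − 6.2) / 6 = 10.97 allows 10 six-monthly visits, giving 3 + 10 = 13 scheduled post-baseline assessments, without the discontinuation visit.

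**Illustration.** Let p be the chance that an otherwise stable subject has an isolated worsening recorded as progression at a visit, independent between visits. The documents give no value; p is an assumption.

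- At least one call in k visits: 1 − (1 − p)^k.
- Two consecutive calls: start with a = 1, b = 0; at each visit a becomes (a + b)(1 − p) and b becomes (previous a) × p; after k visits the probability is 1 − a − b.

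| k | p | At least one call | Two consecutive calls |
|---|---|---|---|
| 3 (to week 27) | 2% | 5.9% | 0.08% |
| 3 | 5% | 14.3% | 0.5% |
| 10 (about 4 years) | 2% | 18.3% | 0.35% |
| 10 | 5% | 40.1% | 2.1% |
| 13 (6 years) | 1% | 12.2% | 0.1% |
| 13 | 2% | 23.1% | 0.5% |
| 13 | 5% | 48.7% | 2.8% |
| 13 | 10% | 74.6% | 10.5% |

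For example, 1 − 0.98^13 = 0.231 and 1 − 0.95^13 = 0.487.

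**The case against.** The best defence is that Section 9.3.1 gives operational content to the general sentence in Section 6: a subject has progressed, for treatment purposes, once two consecutive assessments say so. That reading is possible, but the protocol never states it. Section 9.3.1 itself applies the word progression to each single assessment, and Section 10.1 contains no confirmation step.

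Other parts of the defence stand, and they rule out several stronger readings that a reader might infer.

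- *The endpoint is defined differently in different passages.* It is not. Protocol 11.4.1 and SAP 5.2.1 and 5.2.3 all rely on investigator-assessed progression. The conflict lies in the treatment rules; the endpoint event is under-specified. SAP 5.2.2 is not built on progression.
- *The current protocol keeps treating subjects who have progressed on 6-weekly dosing.* Section 6 speaks of suspected progression, and re-evaluating on suspicion need not contradict stopping on progression. Only footnote k speaks of demonstrated progression. It belongs to the schedule through INT-3, and the Table 2 footnotes are not in the copy read here, so whether it carried over cannot be checked.
- *One grade of fatigue must be recorded as progression.* Attachment 2 is a guide, and the investigator's judgement governs.
- *The primary safety rates are distorted.* Different stopping times change exposure, but SAP 6.1.1 uses each subject's own time at risk for the TEAE overview and selected TEAEs, and SAP 6.1 adds summaries by years of exposure.

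It is also fair that these endpoints are secondary and descriptive, with no hypothesis test.

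**Conclusion.** The point holds in two linked parts. First, treating until progression (3.1, 6, 10.2, SAP 1.1), progression as precluding further study (10.1) and mandatory stopping only after two consecutive progressions (9.3.1) conflict as written and must be reconciled. This does not depend on footnote k or Attachment 2. Second, SAP 5.2.1 and 5.2.3 do not say whether a single or a confirmed progression is the event, so those two results can depend on the stopping rule a site followed.

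The size cannot be estimated from the documents. The contrast of 23% to 49% against 0.5% to 2.8% shows only that the unstated choice can matter. It assumes a 2% to 5% rate with no source, independence between visits and 13 visits for every subject. The visit count is an upper-end case: the cutoff runs from the first subject's enrolment, so later entrants have fewer visits, as do early leavers. Correlated calls would lower the first-call figures. Reading those percentages as an estimate of spurious progression in this trial would be wrong.

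**What to change.** **Protocol.** Reconcile Sections 3.1, 6, 9.3.1, 10.1 and 10.2, the Synopsis and, if it still applies, footnote k, so that they state one rule on progression and treatment, including progression on 6-weekly dosing. Which rule to adopt is the sponsor's clinical decision. Align SAP 1.1 with it.

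**SAP 5.2.1 and 5.2.3.** State that the event is the first investigator-recorded progression, dated at that assessment, whether or not treatment continued. This also settles how progression on 6-weekly dosing with continued treatment is counted.

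**Sensitivity analysis.** Repeat the analysis with progression confirmed at the next assessment and dated at the first. Count subjects who stop at the first progression and have no later assessment as events at that date, and say whether the end-of-treatment assessment can serve as confirmation. Without such a rule, confirmation would be missing exactly where sites stopped at first progression. Report how many first progressions were confirmed, not confirmed or not reassessed, because the last group enters as events by convention.

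**Cost.** Clarifying protocol text, a few SAP sentences and one extra Kaplan-Meier analysis, with no new data collection.

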#### **9.3.2 Laboratory Evaluations**

ESR, CRP, and fibrinogen tests must be performed at the same times as the investigator assessment of disease control. These assessments will be part of the hematology and chemistry panels.

#### **9.3.3 Survival**

For subjects who discontinue study agent, survival status will be assessed twice per year until the subject has been lost to follow-up or has withdrawn consent for the study, or the 6-year data cutoff; whichever occurs first.

#### **9.3.4 Patient-reported Outcomes**

The MCDSS questionnaire will only be completed by the sub-population from the C0328T03 study. The reliability of the MCDSS will be assessed by collecting the completed questionnaire 3 times during the study: at the start of the screening visit, and predose at Cycles 1 and 2.

### **9.4 Pharmacodynamic Biomarker Evaluations**

From serum samples, pharmacodynamic biomarker evaluations include, but are not limited to:

- Quantification of IL-6.
- Assessment of atypical IL-6 splice variants or cleavage fragments may also be performed along with exploratory assessment to compare IL-6 molecular profiles obtained in MCD patients versus commercially available samples from healthy volunteers. Other assessments related to disease and study agent may be performed based on emerging evidence. Planned biomarker analyses will be deferred if emerging study data show less likelihood of providing useful scientific information. Collection of samples for these assessments will be stopped after Amendment INT-4 is implemented.
- CRP (assessed locally as part of clinical laboratory tests using the chemistry laboratory samples).

## 9.5 Glycoform Clearance and In Vivo Protein Degradation Analysis

To evaluate the clearance and degradation of glycoforms after administration of siltuximab, 6 serum samples will be collected from 5 former C0328T03 subjects (a limited number of samples are needed for this analysis).

Siltuximab will be isolated from the serum samples using an anti-Id antibody. The purified protein will then be analyzed by liquid chromatography/mass spectroscopy (LC/MS) techniques (intact mass and peptide mapping) to evaluate the clearance of different glycoforms over time and to determine the circulating levels of different protein degradants.

## 9.6 Antibodies to Siltuximab

Antibodies to siltuximab will be detected using a validated immunoassay. All samples collected for detection of antibodies to siltuximab will also be evaluated for siltuximab serum concentration to interpret antibody response data. Antibodies to siltuximab may also be assessed at other timepoints. Serum samples will be screened for antibodies binding to siltuximab, and the serum titer of confirmed positive samples will be reported. Other immunogenicity analyses may be performed to further characterize the immune responses. Immunogenicity samples will be analyzed at the 6-year data cutoff.

Blood samples to determine antibodies to siltuximab will be collected from all subjects in the study every 12 weeks while receiving siltuximab in conjunction with a dosing visit, and at Week 4, Week 8, and Week 12 following the last administration of siltuximab.

In addition, a blood sample should be drawn, if possible, to determine antibodies to siltuximab any time an infusion related reaction is observed or reported during the study. This sample should be obtained as soon as possible after the reaction. These samples will be stored, and evaluated if deemed necessary. See Section 6.2 for guidelines for management of infusion related reactions.

All samples should be sent to the central laboratory. The sponsor or its designee will test these samples. Instructions for the collection and shipment of these samples are found in the Laboratory Manual.

## 10 SUBJECT COMPLETION/WITHDRAWAL

### 10.1 Completion

A subject will be considered to have completed the study if he or she has completed assessments at the Follow-up Week 4 assessments, or has experienced a clinical endpoint that precludes further study (eg, disease progression).

### 10.2 Discontinuation of Treatment

All subjects will be treated until they progress, withdraw, experience unacceptable toxicity, or until the 6-year data cutoff, whichever comes first. A data cutoff will occur

approximately 6 years after the start of enrollment; however, continued drug supply will be ensured for study subjects who would not otherwise have access to siltuximab outside this clinical study.

If a subject discontinues study agent, obtain end-of-treatment and follow-up assessments, which are the same assessments done at Follow-up Weeks 4, 8 and 12 as applicable. If a subject's study treatment must be discontinued before the end of the treatment regimen, this will not result in automatic withdrawal of the subject from the study. Subjects will have follow-up assessments for survival, occurrence of malignancies, and subsequent MCD therapies until the 6-year data cutoff (see Section 9.3.3).

A subject's study treatment should be discontinued if:

- The investigator believes that for safety reasons (eg, adverse event) it is in the best interest of the subject to stop treatment.
- The subject becomes pregnant.
- The subject initiated any of the prohibited medications requiring discontinuation of treatment (see Section 8.4)

